#### **4.6 Study Endpoints**

##### ***4.6.1 Primary Endpoints***

- Safety and Feasibility

Safety will be evaluated based on the incidence, type and seriousness of adverse events related to the IV administration of test substance as well as the low volume lipoharvest procedure. Adverse events will be assessed according to the NIH Common Terminology Criteria for Adverse Events (CTCAE) v4.0 for scale grading adverse events.

Microbiological testing (culture and sensitivity) will be performed on the ADRC treatment dose produced and administered on site.

Feasibility will be determined as the ability to obtain  $> 100$  mL adipose tissue, obtain  $\geq 20 \times 10^6$  ADRCs, and deliver the prepared cell dose.

##### ***4.6.2 Key Secondary Endpoints***

- Percent epithelialization of the graft at time of first dressing change and day 10 (only if wound dressing change planned) and weeks 2, 3 and 4
- Percent take of the graft at time of first dressing change and day 10 (only if wound dressing change planned) and weeks 2, 3 and 4

Digital photography will be performed at surgery and at each follow-up visit for blinded independent review.

Graft take will be assessed as the area over which vascularization is evident and sufficient anchorage to the underlying tissue exists to support epidermal growth. Take will be expressed as a percentage of the area originally covered by the graft. Percent take should be estimated separately for each graft-treated site.

Both of the above endpoints will be evaluated by (a) visual inspection by the treating surgeon, and (b) standardized digital photography and scoring centrally by a blinded trained assessor.

- Percent of group with complete wound closure at each assessment through to 12 weeks

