## 5.4 Blinding Procedures and Safeguards

The “blinded party” (photographic assessor(s) with no knowledge of the subjects treatment assignment) are those involved in the independent evaluation of the wound digital photographs.

All others involved in the study are considered the “unblinded parties”, meaning those that will or may have knowledge of a patient’s treatment assignment.

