#### **8.10 Post-ADRC Administration Follow-up visits: Weeks 8 ( $\pm 7$ days), 12 ( $\pm 7$ days), 26 ( $\pm 14$ days), and 52 ( $\pm 21$ days)**

The following assessments are to be conducted:

- Physical examination
- Vital signs
- Assessment for adverse events
- Concomitant medications
- Biomarkers (Weeks 8 and 12 only)

The following assessments, tests and questionnaires should be conducted in the order listed below (as applicable to each visit):

- Digital photographs of wound with ruler to indicate the longest length and width
- Occurrence of complete wound closure (Weeks 8 and 12)
- Pruritis VAS
- Patient and Observer Scar Assessment Scale (POSAS)
- Vancouver Scar Scale (Weeks 12, 26 and 52 only)
- Skin elasticity (Delfin SkinElastimeter) measurement (Weeks 12, 26 and 52 only)
- Skin pigmentation (Delfin SkinColorCatch measurement) at Weeks 12, 26, and 52
- Skin hardness (Delfin SkinFibrometer measurement) at Weeks 12, 26, and 52

A summary table of all follow up evaluations is outlined in *Appendix A: Schedule of Procedures*.

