#### ***10.3.2 Key Secondary and Exploratory Endpoint Analysis***

The key secondary endpoints are

- Percent epithelialization
- Graft take
- Proportion of population with complete wound closer

Epithelialization will be assessed by surgeon visual evaluation and blinded independent review of standardized digital photographs. Graft take will be assessed as the area over which vascularization is evident, and sufficient anchorage to the underlying tissue exists to support epidermal growth. Take will be expressed as a percentage of the area originally covered by the graft. Percent take is estimated separately for each of the grafted study sites. The proportion of subjects with complete wound healing will be determined and is defined as skin re-epithelialization without drainage or dressing requirements.

All other secondary endpoints will be treated as exploratory. P-values for each analysis will be computed separately, without any corrections for multiple comparisons. These analyses will be considered as part of the totality of the evidence concerning the safety and effectiveness of the product.

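### Complete wound closure, the only key secondary endpoint followed past week 4, is given no blinded read and no named assessor, although photographs for blinded review are already scheduled at all five closure visits

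*Protocol*

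**What the plan says.** Section 4.6.2 lists percent epithelialization and percent take, and then states: "Both of the above endpoints will be evaluated by (a) visual inspection by the treating surgeon", and by "standardized digital photography and scoring centrally by a blinded trained assessor". The third key secondary endpoint comes after that sentence: "Percent of group with complete wound closure at each assessment through to 12 weeks". Nothing is said there about who assesses it.

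Section 10.3.2 repeats the pattern. "Epithelialization will be assessed by surgeon visual evaluation and blinded independent review of standardized digital photographs"; for closure the section gives a definition only: "The proportion of subjects with complete wound healing will be determined and is defined as skin re-epithelialization without drainage or dressing requirements". The Protocol Summary and Section 8.3 also attach blinded photograph review to epithelialization and not to closure.

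Closure is otherwise a line in the visit lists of Sections 8.9 (weeks 2, 3 and 4) and 8.10 (weeks 8 and 12) and in Appendix A. Photographs are in the same visit lists, and Section 4.6.2 gives their purpose: "Digital photography will be performed at surgery and at each follow-up visit for blinded independent review". Section 5.4 confines blinding to the photograph assessors; "All others involved in the study are considered the" unblinded parties.

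**The concern.** The trial is open-label, and under Section 7 controls have neither fat harvest nor any study treatment, so those at the bedside know the arm. For epithelialization and take the protocol guards against this with a blinded central read. For closure it assigns none, although closure is the more exposed endpoint: besides a visual judgement, its definition includes whether the wound still needs a dressing, and that is settled in the course of care by people who know the allocation.

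Closure is also the only key secondary endpoint followed beyond week 4, so at weeks 8 and 12 no key secondary endpoint has an assigned blinded read. At weeks 2, 3 and 4 a wound could be recorded as closed while the blinded reader scores it less than fully epithelialized, and the protocol does not say how the two relate.

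Section 10.2 says the data are meant to support the design of a larger study of benefit. A closure difference inflated or masked by knowledge of the arm would pass into that design.

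**Working it through.** The protocol states no figure on this point, so there is none to reproduce. The check is mainly textual.

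**Who assesses what**

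| Endpoint | Visits | Blinded photograph read assigned? |
|---|---|---|
| Percent epithelialization | First dressing change, day 10, weeks 2, 3, 4 | Yes (Summary, 4.6.2, 8.3, 10.3.2) |
| Percent take | First dressing change, day 10, weeks 2, 3, 4 | Yes (4.6.2) |
| Complete closure | Weeks 2, 3, 4, 8, 12 (8.9, 8.10, Appendix A) | No section assigns one |

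Photographs are scheduled at all five closure visits. The missing element is the assignment of the read, not the image.

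**Granularity.** Up to 15 subjects at 2:1 gives 15 × 2/3 = 10 ADRC and 15 × 1/3 = 5 controls. One subject is 1/10 = 10 points or 1/5 = 20 points. This would be so under perfect blinding too. If wounds were the unit and every subject had three, one wound would be 1/30 = 3.3 or 1/15 = 6.7 points.

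**Illustration of bias (assumed rates, none from the protocol).** Let p be the true closure rate, equal in both arms, and let m be the share of unclosed ADRC subjects called closed. The ADRC arm then shows p + m(1 − p), a spurious difference of m(1 − p). If closed controls are also called open at rate m, controls show p(1 − m), and the difference becomes m(1 − p) + mp = m.

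| True closure p | Difference in points, ADRC error only (m = 10, 20, 30%) | Errors in both arms (same m) | Chance of an observed ADRC advantage of at least 20 points: no error, then m = 20% (ADRC error only) |
|---|---|---|---|
| 30% | 7, 14, 21 | 10, 20, 30 | 28.4%, 49.8% |
| 50% | 5, 10, 15 | 10, 20, 30 | 29.5%, 43.0% |
| 70% | 3, 6, 9 | 10, 20, 30 | 27.1%, 34.9% |

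The last column is an exact binomial enumeration of 10 versus 5 subjects. With ADRC-side error only, Fisher's exact test (chosen here for illustration) gives p < 0.05 in at most 7.4% of trials, at p = 30% and m = 30%. A false significant result is therefore unlikely; the exposure is in the estimate.

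**Added reading.** Weeks 2 to 4 are already read for epithelialization. Weeks 8 and 12 add 15 × 2 = 30 to 45 × 2 = 90 image sets, for the 15 to 45 wounds of Section 4.3.

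**The case against.** A reader might infer that closure is judged only by unblinded site staff. The documents do not say so. No section names the assessor. Section 4.6.2 says photographs at every follow-up visit are for blinded review, and at weeks 8 and 12 neither epithelialization nor take is scheduled, so review there must serve some other purpose. Closure is one candidate; scar height, which the oblique images in Section 8.7.2 are meant to show, is another. Section 8.3 leaves detailed instructions to a reference manual that is not at hand. What stands is narrower: the protocol assigns the blinded read to two endpoints and to no part of the third. A general purpose for the images is not an assignment of scoring.

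A reader might also take the 10- and 20-point figures as the size of the bias. They are not, and the misclassification rates above are assumptions.

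It is fair to add that the primary endpoints are safety and feasibility, that Section 10.2 disclaims power, and that the blinded epithelialization scores at weeks 2 to 4 offer a partial check on closure in that period. These points limit the impact but do not close the gap, least of all at weeks 8 and 12. Nor is this something to leave to a statistical analysis plan: who assesses an endpoint is a matter of design, and the protocol fixes it for the other two.

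Finally, photographs cannot reliably show drainage or the need for a dressing. That is correct and limits what any blinded read can achieve. A healed control wound that staff keep dressed would still count as not closed.

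**Conclusion.** The point holds in this form: as written, complete closure is open to assessment bias, because no part of it is assigned to the blinded assessor, everyone else is unblinded, and its definition depends partly on dressing status. This rests on reading Sections 4.6.2, 5.4, 8.9, 8.10 and 10.3.2 together; no single sentence states it.

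The bias cannot be sized from the documents. Under the assumed error rates of 10 to 30%, the spurious difference runs from 3 to 21 points with error in the ADRC arm only, and from 10 to 30 points with errors in both arms. The impact is modest: a secondary endpoint in an unpowered pilot, with little risk of a falsely significant test. What is at stake is a closure estimate that feeds the planning of the larger study. The change is worth making because the images already exist in the schedule. A reader might infer that a blinded read would make closure an unbiased endpoint; it would not, since the drainage and dressing part would remain unblinded.

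**What to change.** Amend Sections 4.6.2 and 10.3.2 as follows.

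- The existing blinded assessor reads re-epithelialization status (complete or not) from the photographs already scheduled at weeks 2, 3, 4, 8 and 12.
- That blinded result is reported on its own by arm, next to protocol-defined closure. In the latter, the re-epithelialization component comes from the blinded read, and drainage and dressing status come from the site record. The surgeon-only version is supportive.
- The text states that the drainage and dressing component stays unblinded and may still bias closure in either direction. Dressing care is not changed.
- The unit is the subject, as in Section 10.3.2, with a stated rule for subjects with two or three qualified wounds. Section 8.3 also refers to a percentage of wounds and should be aligned.
- Unreadable photographs are reported as missing, in keeping with the no-imputation rule of Section 10.6, with the on-site call used in a sensitivity analysis.

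The cost is protocol wording plus 30 to 90 further image sets for the same reader. No visits, photographs or staff are added. The downside is some unreadable images, and in about 15 subjects each missing outcome counts.

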Indication	Celution® System is intended for the preparation of autologous adipose-derived regenerative cells (ADRCs) for intravenous use as an adjunct to autologous split thickness skin grafts used in the current standard treatment of full thickness and deep partial thickness thermal burn injuries
Post Procedure Evaluations	Evaluations at early dressing changes (time of first dressing change, day 10 ( $\pm 2$ ) days and weeks 2 ( $\pm 3$ days), 3 ( $\pm 3$ days), 4 ( $\pm 3$ days), 8 ( $\pm 7$ days), 12 ( $\pm 14$ days), 26 ( $\pm 14$ days) and 52 ( $\pm 21$ days) post-grafting
Treatment Arm	Adjunct to thermal burn skin wound coverage with autologous meshed split thickness skin graft (STSG) delivered intravenously on the same day as STSG. Dose: $20 \times 10^6$ ADRCs

Primary Endpoint	Safety and Feasibility 
 
Safety will be evaluated based on the incidence, type and seriousness of adverse events related to the IV administration of test substance as well as the low volume lipoharvest procedure.
 
Feasibility will be determined as the ability to obtain > 100 mL adipose tissue, obtain <math>\geq 20 \times 10^6</math> ADRCs, and deliver the prepared cell dose.
 

Key Secondary Endpoints	
 
Percent epithelialization of the graft at time of first dressing change, day 10 and weeks 2, 3 and 4 post grafting (assessed by surgeon visual evaluation and blinded independent review of standardized photographs)
 
Percent take of the graft at time of first dressing change and day 10 and weeks 2, 3 and 4
 
Percent of group with complete wound healing at weeks 2, 3, 4, 8 and 12
 

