### **3 RATIONALE**

Patients with thermal wounds often require intensive management and have the risk of incomplete wound closure, prolonged period to wound closure, dysfunctional tissue healing (i.e. contractures, keloids) and infection. Such injuries may ultimately lead to chronic pain and disability. For digits and limbs, progressive injury may result in amputation. In addition, more rapid and complete wound healing following acute burns could reduce other complications and decrease the time spent in specialized hospital units. Cells present within the subject's own adipose tissue, ADRCs have the potential to improve healing following thermal injury by potentially reducing inflammation, improving restoration of blood flow, and stimulating local repair cells. Preclinical studies performed by Cytori in a full thickness thermal injury porcine model have demonstrated local and systemic delivery of autologous ADRCs without a scaffold increase wound re-epithelialization. Using a similar model but with Integra® skin substitute, local delivery of ADRCs is associated with improved wound tissue vascularity and maturation. In previous clinical studies, these cells have a favorable safety profile in acute myocardial injury, heart muscle damage, breast deformity following lumpectomy, and OA of the knee.

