### **4 STUDY DESIGN**

#### **4.1 Study Overview**

The RELIEF Trial is a prospective, open-label, parallel group, usual care controlled, multi-center randomized (2:1, active: usual care alone) safety and feasibility study targeting thermal burns. Subjects will have at least one deep partial or full thickness burn wounds of  $\geq 250 \text{ cm}^2$  that is to be autografted with a meshed split thickness skin graft (STSG). Subjects randomized to ADRCs will undergo small volume fat harvest (100 to 150 mL) performed at initiation of general anesthesia for scheduled burn surgery followed by intravenous delivery of ADRCs within 4 hours following completion of Celution processing. The lipoaspirate will be processed in the Celution® System to isolate and concentrate ADRCs.

Following informed consent and initial screening assessments, eligible subjects will undergo pre-operative testing. On the procedure day, subjects will be randomized to ADRCs (with usual care) or usual care alone. Low volume lipoharvest will only be performed on subjects randomized to ADRCs in order to obtain 100-150 mL lipoaspirate, which will then be transferred to the Celution® System for processing to isolate and concentrate ADRCs for same-day administration. All treatment will be delivered in a total volume of 10 mL which will be delivered by slow intravenous administration into a peripheral vein.

Following surgery, subjects will be evaluated at time of first dressing change, day 10 ( $\pm 2$ ) (only if wound dressing change planned) and weeks 2 ( $\pm 3$  days), 3 ( $\pm 3$  days), 4 ( $\pm 3$  days), 8 ( $\pm 7$  days), 12 ( $\pm 14$  days), 26 ( $\pm 14$  days), and 52 ( $\pm 21$  days).

All subjects will undergo digital photography of the wounds, clinical evaluations, microbiology and laboratory testing prior to and after the procedure as outlined in *Section 9.0, Study Visit Requirements*, and in the *Schedule of Procedures (Appendix A)*.

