## 4.3 Sample Size

Up to a total of 15 subjects will be enrolled. Each patient may contribute up to three qualified wound

areas for the analysis. If more than one wound is identified, each must be noncontiguous with the other(s). Therefore, between 15 and 45 wounds will be evaluated. Wound areas that have been treated with a biologic dressing such as Alloderm® or Integra® are not qualified for analysis. However, a wound area that receives excision and grafting as described in this protocol without the application of a biologic dressing may be qualified even if other wound areas in the subject are not qualified because they have been treated with a biologic dressing.

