### 8.3 Burn Evaluations

The physical characteristics of the selected burn areas and the graft (up to 3 per subject) as well as the subjective evaluation of symptoms will be evaluated using several assessment tools. The assessment tools are listed below and detailed information and instructions provided in the *Study Reference Manual*. Planned study days are listed below but an acceptable range of days (±) is in the schedule of events.

- Percent epithelialization at early dressing changes (estimated time of first dressing change and day 10 after graft application and at weeks 2, 3 and 4 (by surgeon evaluation and blinded independent review of standardized photographs)
- Percent take of the graft at early dressing changes (estimated time of first dressing change and day 10 after graft application (if wound dressing must be changed) and at weeks 2, 3 and 4
- Occurrence of complete wound healing at each assessment weeks 4 to 12
- Transepithelial water loss at weeks 2, 3 and 4
- Wound pain VAS at time of first dressing change and day 10 and weeks 2, 3 and 4
- Pruritis VAS at 3, 4, 8, 12, 26 and 52 weeks
- Patient and Observer Scar Assessment Scale (POSAS) at 3, 4, 8, 12, 26 and 52 weeks
- Vancouver Scar Scale at 12, 26, and 52 weeks
- Skin elasticity measurement at 12, 26 and 52 weeks (Delfin SkinElastimeter)
- Skin pigmentation (Delfin SkinColorCatch) measurement at weeks 12, 26, and 52
- Skin hardness (Delfin SkinFibrometer) measurement at weeks 12, 26, and 52

- Percent of wounds with complete wound closure at weeks 2, 4, 8 and 12
- Digital photography of treated wounds on day 1 and each follow up visit
- Biomarkers related to burn injury will be assessed from 4-5mL blood (serum) samples drawn at baseline (prior to treatment), time of first dressing change and day 10 and weeks 2, 3, 4, 8 and 12 post-ADRC administration.

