### 10.3 Data Analyses

Safety and efficacy endpoints will be summarized by treatment group using descriptive statistics (n, mean, SD, median, minimum and maximum), for quantitative variables and frequencies and percentages for categorical variables.

For quantitative efficacy variables, the change from baseline to each post-baseline time point will be analyzed using Student's t-test. For each endpoint, the treatment groups will be compared using two-sided tests at the alpha=0.05 level of significance.

The final dataset includes grafts with different mesh size (for example; 2:1 and 3:1). While the study is not powered for analysis of efficacy, data analysis for comparison between subjects receiving usual care and those receiving usual care plus ADRCs with respect to exploratory endpoints associated with healing (e.g.: percent epithelialization, pigmentation, hardness, Vancouver Scar Scale) will be stratified by mesh size (for example: 2:1, 3:1, 4:1, and all grouped).

Subjects randomized to the ADRC-treatment arm who undergo liposuction but who are not treated with ADRCs because the ADRCs do not meet release criteria may be followed up for the full duration of the study. Such subjects will be (a) included in the full data analysis for feasibility, (b) analyzed separately for safety, (c) analyzed in the ITT group for efficacy, and (d) excluded from the PTE group for efficacy.

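### Complete wound closure, a key secondary endpoint, has at least three conflicting visit lists and no consistent unit, and is stated only as a percentage per visit although faster healing is part of the postulated benefit.

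*Protocol*

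**What the plan says.** The closure endpoint is described in several places in the Protocol:

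- Summary, key secondary endpoints: "Percent of group with complete wound healing at weeks 2, 3, 4, 8 and 12".
- Section 4.6.2: "Percent of group with complete wound closure at each assessment through to 12 weeks".
- Section 8.3, one bullet: "Occurrence of complete wound healing at each assessment weeks 4 to 12".
- Section 8.3, a later bullet in the same list: "Percent of wounds with complete wound closure at weeks 2, 4, 8 and 12".
- Sections 8.9 and 8.10 and the Appendix A grid: closure is recorded at weeks 2, 3, 4, 8 and 12. It is not among the assessments at the first dressing change or Day 10 (section 8.8).
- Section 10.3.2: the result is the proportion of subjects with complete healing, defined as re-epithelialized skin with no drainage and no need for dressings.

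On analysis, section 10.3 says "For each endpoint, the treatment groups will be compared using two-sided tests at the alpha=0.05 level of significance". No visit is named as the one that counts, and no contrast combines the visits. On purpose, section 3 argues that "more rapid and complete wound healing following acute burns could reduce other complications", and sections 9.8 and 9.10 also speak of earlier or accelerated healing. On size, section 4.3 states "Up to a total of 15 subjects will be enrolled", and section 4.1 describes the trial as "randomized (2:1, active: usual care alone" by arm. Each subject may contribute up to three wounds.

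**The concern.** There are two linked faults. First, a reader cannot tell from the text which visits or which unit define this endpoint. A programmer working from section 8.3 would build a different table from one working from the Summary. With up to three wounds per subject, a percentage of wounds and a percentage of subjects are different quantities. Wounds in one subject are also not independent.

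Second, faster healing is a statement about when closure happens. A row of separate percentages does not summarize timing, and the most telling visit depends on a healing rate nobody knows in advance. Section 10.2 says the trial exists to help design a larger, powered study. An inefficient or ambiguous closure result weakens that planning use, although no success claim rests on it.

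**Working it through.** **Visit lists side by side**

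| Source | Visits (weeks) | Unit |
|---|---|---|
| Summary | 2, 3, 4, 8, 12 | group |
| 8.9, 8.10, Appendix A | 2, 3, 4, 8, 12 | not stated |
| 4.6.2 | each assessment to 12 | group |
| 8.3, occurrence bullet | 4, 8, 12 | not stated |
| 8.3, percentage bullet | 2, 4, 8, 12 | wounds |
| 10.3.2 | none given | subjects |

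Three lists differ for certain. Section 4.6.2 fits the first list if assessment means closure assessment.

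**Inputs for the size of the effect.** From the Protocol: 15 subjects at 2:1, so 15 × 2/3 = 10 and 15 × 1/3 = 5; two-sided 0.05; visits at weeks 2, 3, 4, 8, 12. The Protocol states no power, effect size or closure rate, so there is no figure to reproduce. Assumed, not in the documents: one closure time per subject, Weibull shape 1.5, control median m of 3 to 8 weeks, closure hazard ratio 3, no dropout.

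**Formulas.** Control closure by week t: F0(t) = 1 − exp[−ln 2 × (t/m)^1.5]. ADRC closure: F1(t) = 1 − [1 − F0(t)]^3.

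With 10 versus 5, Fisher's test favors ADRC at p < 0.05 only when closures are at least 6 of 10 against 0 of 5, at least 9 against 1, or 10 against 2.

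**Worked case, m = 8, week 8.** F0 = 0.50 and F1 = 1 − 0.5^3 = 0.875.

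- P(0 of 5) × P(at least 6 of 10) = 0.0313 × 0.9955 = 0.031
- P(1 of 5) × P(at least 9 of 10) = 0.1563 × 0.639 = 0.100
- P(2 of 5) × P(10 of 10) = 0.3125 × 0.263 = 0.082

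The sum is 0.213. Cells favoring control add nothing visible.

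**All visits, power in %.** Fisher values are exact. The log-rank column is a permutation test over all 3,003 allocations, 3,000 simulated trials per row, simulation error about 0.9 points.

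| Control median | Wk 2 | Wk 3 | Wk 4 | Wk 8 | Wk 12 | Log-rank |
|---|---|---|---|---|---|---|
| 3 weeks | 17.0 | 21.3 | 16.4 | 0.1 | 0.0 | 44 |
| 4 weeks | 13.3 | 18.0 | 21.3 | 2.2 | 0.0 | 42 |
| 6 weeks | 3.8 | 13.3 | 17.0 | 16.4 | 2.2 | 39 |
| 8 weeks | 0.9 | 6.1 | 13.3 | 21.3 | 11.4 | 42 |

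The best single visit moves from week 3 to week 8 as healing slows. If any of the five Fisher tests may count, power is about 32 to 34%, so the gain over that looser reading is smaller.

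**Smaller effect.** With ADRC closure times 0.67 of control (for shape 1.5 a hazard ratio of 0.67^−1.5 = 1.8), the best single visit has about 7% power. The log-rank test has about 14 to 16% for control medians of 3.5 to 8 weeks.

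**Error with no effect.** At shape 1.5, at least one of the five Fisher tests is significant in about 5% of trials. The permutation log-rank test rejects in about 4 to 5%.

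**Does the list matter?** With control median 2.5 weeks, shape 3 and time ratio 0.67, the chance of any significant visit is 27.9% for weeks 2, 3, 4, 8, 12; 19.6% for weeks 2, 4, 8, 12; and 0.2% for weeks 4, 8, 12. With a median of 8 weeks and the same shape and ratio it is 27.1% for all three. The choice of list matters when healing is fast and hardly at all when it is slow.

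**The case against.** The strongest reply is that collection is not in doubt: the Summary, sections 8.9 and 8.10, and Appendix A agree, so the visit conflict lies in two bullets of section 8.3. Closure is secondary in a pilot that sections 10.2 and 10.3 describe as not powered, and section 10.1 leaves analysis detail to a SAP that is not shown. Nothing in the Protocol bars a time-to-closure analysis. The rationale also speaks of complete healing, which the week 12 percentage addresses directly.

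Most of this stands, and it limits the point. It does not remove the contradictions in visits and unit, which the Protocol itself has written down. Lack of power is also a reason to use the closure data well, not a reason to ignore their ordering.

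A reader might infer more than the documents support:

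- *Four conflicting lists.* Section 4.6.2 would be a fourth only if read to include the first dressing change and Day 10, where closure is not scheduled.
- *Late visits are uninformative.* This depends on healing rates the documents do not give. Week 8 is the best single visit if the control median is near 8 weeks.
- *Serious false-positive inflation.* A 13 to 17% chance of some significant visit arises only if a t-test or ANOVA is applied to a yes/no outcome. Section 10.3 assigns the t-test to quantitative variables; only the Summary's general ANOVA line could suggest otherwise. With Fisher tests the figure is about 5%.

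**Conclusion.** The point holds as a should-fix matter of consistency and efficiency for a key secondary endpoint. The conflicts in visits and unit are certain from the text. The efficiency loss is conditional: under the stated assumptions, about 17 to 21% power for the best single visit against about 42% for one log-rank test, and about 7% against 14 to 16% for the smaller effect. It would be wrong to infer that the change makes the trial adequately powered; it does not. What it supplies is one deciding contrast that does not depend on guessing the informative visit. The primary safety and feasibility endpoints are unaffected.

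**What to change.** 1. Visits: in sections 4.6.2 and 8.3, state closure at weeks 2, 3, 4, 8 and 12, as in Appendix A, and merge the two bullets in 8.3.
2. Unit: in the Summary and sections 4.6.2, 8.3 and 10.3.2, make the subject the unit, closed when all of the subject's qualified wounds are closed. Any per-wound analysis must account for clustering within subject.
3. Contrast: in section 10.3.2, name one between-arm comparison, time from grafting to the first scheduled visit with complete closure through week 12. Use an exact permutation log-rank test with Kaplan-Meier curves, censoring subjects not yet closed at their last assessment.
4. Keep the per-visit percentages as description, including week 12 for completeness of healing.

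The cost is Protocol and SAP wording. No new visit, measurement or subject is needed. The downside is small: closure time is known only to the visit interval, and wounds that reopen after first closure must be listed separately.
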